To limit bias, the trial is double-blind, keeping all participants, investigators, and all staff involved in the conduct of the trial blinded to the treatment administered. Eligible participants for this trial will be randomly assigned (based on a pre-determined computer-generated list) to 3 groups to receive either of the study interventions. All interventions are supplied as unit dose unpreserved formulations commercially available in Australia and registered on the ARTG. Intervention categories will be pre-packed in sealed envelopes and randomly labelled (intervention A, intervention B, and intervention C). Each envelope will have a sufficient amount of dosage for the treatment period.

- A schematic diagram of trial design is shown in Figure 2.

[figure not shown]

Figure 2 Trial flow diagram

8. Sample Size

The plan is to enroll 90 subjects to complete the trial.

The overall sample is comprised of the following samples from each of the participant groups:

1. **Participant Group 1** [Topical antihistamine + mast cell stabiliser]: [30 participants]
2. **Participant Group 2** [Topical corticosteroid]: [30 participants]
3. **Participant Group 3** [Topical ocular lubricant]: [30 participants]

Sample size calculation was undertaken using GPower 3.1. The nominated sample is based on based on the expected effect size at the central cornea dendritic cell density (0.512), from a previous study [1], alpha (0.05), and power of (0.8). The sample size will be 25 participants in each arm. The sample size will be adjusted by 20% to compensate for expected withdrawals. Therefore, the total sample size would be 90 participants for all arms, 30 participants in each arm, to ensure 75 participants complete the study after accounting for 20% drop out rate. This sample size is sufficient to meet the research aims and will address all the research questions. By this sample size, the power calculation reveals that this sample size will allow for statistically significant results.

1. Tajbakhsh, Z., et al., *Increased dendritic cell density and altered morphology in allergic conjunctivitis*. Eye (Lond), 2023.

9. Selection and Withdrawal of Subjects

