9.6 Withdrawal of Consent or Participant

- The participants have the right to withdraw from the trial at any time for any reason, without the need to justify their decision. However, the Investigator should record the reason for the patient's withdrawal, if possible. The investigator also has the right to withdraw participants.
- Participants will be withdrawn in the following circumstances:
- A participant's desire to withdraw for any reason.
- Loss to follow-up (every effort must be made to contact the participant; a certified letter must be sent or phone calls)
- An adverse event which, in the opinion of the Investigator and/or Sponsor, necessitates withdrawal.
- A participant's substantial non-compliance (e.g., visits non-compliance) after the start of the trial.
- The investigator's opinion that continuing the participant in the trial is not appropriate. The investigator may withdraw a participant at any time if it is considered to be in the participant's best interest.
- Participants suffering a worsening in disease are to be withdrawn. Worsening will be defined as an increase from the last visit in symptoms and signs score. Such worsening should be evaluated by the investigator and confirmed by slit lamp examination (no improvement or worse symptoms and signs) prior to deciding whether or not to withdraw the patient.

In case the participant has withdrawn consent, no new data can be entered into the record form. Any withdrawal must be fully documented in the report form and registered in as discontinued. If the reason for discontinuation is an adverse event, the specific event will be recorded in the report form. Withdrawn participants will not be replaced.

In case the investigator becomes aware of any serious adverse events (SAEs) or related non-serious adverse events in a withdrawn participant after trial completion these will be reported to HREC.

HREC may temporarily or permanently discontinue the trial at an investigational site at any time for safety, ethical, compliance or other reasons. If this is necessary, HREC will endeavour to provide advance notification to the site. If the site or trial is suspended or discontinued, the Investigator/Investigative Staff will be responsible for promptly informing HREC that this has happened.

10. Treatment of Subjects

Participants will undergo the following procedures:

- **Skin Prick Testing:**

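### Section 8 allows for dropout by multiplying by 1.2, so 90 enrolled gives 72 expected completers at 20% dropout, not the 75 stated

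*Protocol*

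**What the plan says.** Section 8 (Sample Size) gives the requirement before dropout: "The sample size will be 25 participants in each arm". It then describes the allowance: "The sample size will be adjusted by 20% to compensate for expected withdrawals". The result is that "the total sample size would be 90 participants for all arms, 30 participants in each arm", and the stated aim is "to ensure 75 participants complete the study after accounting for 20% drop out rate".

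The inputs behind the 25 are the software (GPower 3.1), an effect size of 0.512 for central corneal dendritic cell density taken from a previous study, alpha 0.05 and power 0.8. The section does not name the test, its sidedness, or the metric of the effect size.

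Three other places bear on the point. Sections 7 and 13 give 1:1:1 allocation, and Section 7 makes clear that 90 is the number randomly assigned. Section 9.6 says "Withdrawn participants will not be replaced". Section 9.4 says that measurements and confocal images obtained before a withdrawal of consent are kept and analysed.

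**The concern.** The section states an enrolment (90), a dropout rate (20%) and a number of completers (75). Any two of these fix the third, and the three given do not agree. The cause appears to be a common slip: the requirement was increased by the dropout percentage, when it should have been divided by the proportion expected to remain.

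The figure matters because the section goes on to say that the sample size is sufficient for the research aims. If 25 per arm is what 80% power requires, the stated dropout rate leaves fewer than that. Because withdrawals are not replaced, the trial has no mechanism for making up a shortfall once it occurs.

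**Working it through.** **Inputs.** All are from Section 8 except the last two: 25 evaluable per arm (3 × 25 = 75), a 20% adjustment and dropout rate, 30 per arm and 90 enrolled, 75 completers; 1:1:1 allocation (Sections 7 and 13); no replacement (Section 9.6).

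**1. Reproducing the plan's enrolment.** Formula: n × (1 + d).
- 25 × 1.2 = 30 per arm; 3 × 30 = 90. This matches exactly, so it is very likely how 90 was obtained.

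**2. Completers that 90 gives at 20% dropout.** Formula: N × (1 − d).
- 90 × 0.8 = 72 in total; 30 × 0.8 = 24 per arm.
- Shortfall: 75 − 72 = 3 in total; 25 − 24 = 1 per arm.

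**3. Dropout rate at which 75 of 90 complete.**
- 1 − 75/90 = 0.167, or 16.7%.

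**4. Enrolment needed to expect 75 completers at 20% dropout.** Formula: N / (1 − d).
- On the total: 75 / 0.8 = 93.75, so 94.
- With equal arms and 25 expected in each: 25 / 0.8 = 31.25, so 32 per arm and 96 in total, giving 96 × 0.8 = 76.8 expected completers.

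**5. How far 75 is from being ensured.** Assume each participant drops out independently with probability 0.2. The binomial probability that at least 75 complete is:

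| Enrolled | P(at least 75 complete) |
|---|---|
| 90 | 0.26 |
| 94 | 0.58 |
| 96 | 0.73 |

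Even the corrected enrolments only make 75 the expected number or slightly less than it. None of them ensures it.

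**6. Effect on power (conditional).** The test behind 25 is not stated, so this step rests on assumptions. Two candidates come close to 25 with alpha 0.05 and power 0.8:
- One-sided paired or one-sample t-test with d = 0.512, from the noncentral t distribution with n − 1 degrees of freedom and noncentrality d√n. This needs n = 25. Power is 0.800 at 25 and 0.785 at 24.
- Three-group one-way ANOVA with f = 0.512/√2 = 0.362. This needs 26 per arm. Power is 0.791 at 75 in total and 0.772 at 72.

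Under either, losing one participant per arm costs about 1.5 to 2 percentage points of power. Other readings of 0.512 do not give 25: a two-sided two-sample t-test with d = 0.512 needs 61 per arm, and a three-group ANOVA with f = 0.512 needs 14. The text alone therefore does not identify the calculation.

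**The case against.** The best defence is that the 20% is simply an inflation factor, in which case 25 × 1.2 = 30 is exactly what was intended. That would work if the section stopped at the adjustment. It does not, because the next step calls the same 20% a dropout rate and derives 75 completers from it.

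A stronger defence concerns importance, and most of it stands. The gap is one participant per arm. Completers are not stated to be the analysis set for the primary endpoint: Section 9.4 retains data collected before withdrawal, and Section 18 analyses density with a linear mixed model, which can use participants with incomplete visits. This softens the consequence for the analysis, but it does not make the completer figure true.

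A reader might also infer more than the documents support:
- **That the shortfall is bound to happen.** Non-replacement means that lost participants are not refilled, but 75 or more will still complete if actual loss is 16.7% or less. The supportable statement is that 75 is neither expected nor ensured at 20%.
- **That the plan used a one-sided paired test.** That test reproduces 25, but the protocol names no test, so it remains an assumption.
- **That 75 completers require 96 enrolled.** The total requires 94; 96 follows only from equal arms with 25 expected in each.
- **That "The plan is to enroll 90 subjects to complete the trial" promises 90 completers.** It can be read as enrolling 90 in order to carry out the trial, and Section 7 treats 90 as the number randomised. This is loose wording and not a second numerical error.

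**Conclusion.** The point holds as an arithmetic error with a small effect. At the stated 20% dropout, 90 enrolled gives 72 expected completers (24 per arm), not 75 (25 per arm). The enrolment of 90 matches 75 completers only at 16.7% loss. This conclusion uses only figures in Section 8 and does not depend on how the 25 was derived.

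The size is three completers in total. If the 25 came from a one-sided paired or one-sample t-test with d = 0.512, power at 24 is about 78.5% instead of 80%; that figure is conditional on the assumed test. The slip should not be read as showing that the trial is materially underpowered: the loss is one participant per arm, and partial data from those who withdraw are retained. Whether 25 per arm is itself the right requirement is a separate question that the dropout arithmetic does not settle.

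**What to change.** Keep 90 and correct the statement in Section 8. Either of these would do:
- 90 randomised gives 72 expected completers (24 per arm) at 20% dropout; or
- 90 randomised allows for 16.7% dropout while leaving 75 expected completers (25 per arm).

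With either wording, replace ensure with expect. If the first is used, restate the power at 24 per arm with the test that the sponsor used to obtain 25, naming the test, its sidedness and the effect-size metric. Optionally, change the opening sentence of Section 8 to say that 90 will be randomised.

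The cost is a text change and one rerun of the existing power calculation. Recruitment, design and analysis stay as they are, and the stated figure becomes slightly less favourable. If the sponsor does want to expect 75 completers at 20% loss, enrolment would have to rise by 4 to 94, or by 6 to 96 with equal arms. The shortfall is too small to make that necessary.

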9.1 Inclusion Criteria

1. Be at least 18 years of age or older.
2. Positive result in the skin prick test.
3. All participants must have current active allergic conjunctivitis symptoms (including itchy eyes or watery eyes or burning feeling or feeling like there is dirt or grit in your eyes) or signs (including redness or conjunctival chemosis or conjunctival papillae or conjunctival follicles), with or without a prior diagnosis of ocular allergy or hay fever.
4. Able to read and comprehend English and give informed consent as demonstrated by signing a record of informed consent.

9.2 Exclusion Criteria

1. Severe allergic conjunctivitis (reflective from the total symptoms scores of the Mini-RQLQ and OSDI questionnaires) including vernal keratoconjunctivitis and atopic keratoconjunctivitis.
2. Negative result in the skin prick test.
3. Severe asthma.
4. Severe eczema.
5. Past anaphylactic episode.
6. Previous allergic reaction to any component of topical eyedrops used in this study including benzalkonium chloride preservative.
7. Pregnant or breastfeeding/childbirth within three months from the date of recruitment.
8. Regular contact lens wear (wearing contact lenses for at least two or more full days in a week).
9. All other ocular surface diseases except allergic conjunctivitis.
10. Ocular diseases that involve the cornea.
11. Active intraocular inflammation.
12. History of corneal refractive surgery.
13. Systematic conditions affecting the ocular surface include diabetes, thyroid disorder, rheumatoid arthritis and Sjögren syndrome.

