9.4 Screening

The first email exchange between participants and the research investigators will entail a copy of the Participant Information Statement and Consent Form, which demonstrates the screening procedure, and key inclusion and exclusion criteria outlined in section 9. Once they pass the screening procedure, a date will be set for the participant visit. The participants will read and sign the informed consent form prior to data collection. Ineligible subjects will be notified and excluded from the study immediately. For participants who withdraw their study consent, no additional data will be collected. However, measurements and confocal microscopy collected before the withdrawal will be retained and analysed.

Screening process:

After participants have contacted the investigators regarding their interest, an email will be sent to the participants as part of a screening procedure. This will include questions regarding the key inclusion and exclusion criteria.

The investigators will conduct two eligibility phases (phase 1: eligibility questionnaires and phase 2: eligibility confirmation by the Skin Prick Test results) on the screening day. Phase one takes place at the School of Optometry and Vision Science, UNSW. The investigator will ask questions about ocular allergy or hay fever symptoms including itchiness and watery eyes, sneezing, or running nose, and interested participants will be asked to answer additional questionnaires to assess their eligibility for the study. They will take part in a preliminary examination which includes visual acuity assessment and ocular health check in order to exclude undiagnosed eye diseases.

In the second phase, a Skin Prick Test which takes approximately 15 minutes to complete will be conducted on the same visit day, under medical supervision at the UNSW Health Service After determining the eligibility of the participants and signing of the consent form. Included participants will be asked to complete a washout period of 1 week duration for which they will be given commercially available ocular lubricant eyedrops (Blink Intensive Tears eyedrops, ARTG ID:158805) and will be asked to install two drops daily in both eyes for 1 week. Eligible participants with active allergic conjunctivitis based on current active allergic conjunctivitis symptoms (including itchiness or watery eyes or burning feeling or feeling like there is dirt or grit

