This test is for the confirmation of allergy eligibility as set by the inclusion criteria and will be conducted at phase two of the eligibility examination as described in section 10.4. A standard Skin Prick Test for common Sydney-based region indoor and outdoor aeroallergens will be conducted on each participant using extracts of ten chosen allergens (Stallergenes, Antony, France). Allergens will include four grass pollens (Rye: *Lolium perenne*, Bermuda: *Cynodon dactylon*, Paspalum: *Paspalum notatum* and Johnson: *Sorghum halepense*), two tree pollen (Cypress: *Cupressus arizonica* and Olive: *Olea europaea*), two dust mites (DP: *Dermatophagoides pteronyssinus* and Farinae: *Dermatophagoides farinae*), plant pollen (Plantain: *Plantago lanceolata*), the mold *Alternaria* and cat and dog dander.

A drop of each allergen will be placed on the forearm, and a slight skin prick will be made using a lancet at the same spot to allow the allergen to be absorbed by the skin. Ten minutes later, the skin's allergic reaction will be determined by measuring the size of the hive formed on the skin.

- **History taking:**

A review of demographics, ocular and medical history will be conducted verbally.

- **Questionnaires**

Participants will be asked to complete questionnaires related to eye and nose allergy symptoms and participants' quality of life: Numerical Rating Scale (NRS) [1, 2], Mini Rhinoconjunctivitis Quality of Life Questionnaire (Mini-RQLQ) [3], Ocular Surface Disease Index (OSDI) [4], Aston University Allergy Questionnaire (AUAQ) [5], the dry eye questionnaire for the detection of dry eye (Dry Eye Questionnaire: DEQ-5) [6], and the Eye Allergy Patient Impact Questionnaire (EAPIQ) [7]. Changes in symptoms and signs will be recorded, reported and analysed from both eyes as appropriate.

- **Visual acuity assessment**

Measurement of the standard of vision achieved with the participants' usual spectacle correction in place (if any), will be measured using standard letter charts. Measurements will be taken separately for each eye. Pinhole acuity will be attempted for those without 6/6 vision.

- **The Perkins Tonometer**

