The Perkins tonometer is a handheld applanation model used to measure intraocular pressure. The principle of applanation tonometry is based on the force required to flatten a certain area of the spherical surface of the cornea is the same as the pressure inside the eye. The Perkins tonometer is a very popular handheld applanation tonometer used in humans.

- **The Oculus Keratograph 5M (K5)**

This is an advanced corneal topographer with a built-in real keratometer and a colour camera optimized for external imaging. In our study the tear film break-up time will be measured automatically and non-invasively.

- **Slit lamp biomicroscopy**

The ocular surface and anterior segment will be examined using a slit lamp biomicroscope and ocular surface signs, including conjunctival and limbal redness (graded using the Cornea and Contact Lens Research Unit (CCLRU) grading scale), conjunctival chemosis, papillae and follicles (graded using the Japanese grading scale for allergic conjunctivitis [8]).

- **Ocular staining**

A wetted fluorescein strip (harmless yellow dye) and a wetted lissamine green strip (harmless green dye) will be then gently touched to the fornix of the lower lid. Participants will be asked to blink continuously to enable the smooth spreading of the stain over the eye, allowing for the evaluation of any surface defects. Ocular surface (corneal and conjunctival) staining will be assessed using the Oxford grading scale [9]. These dyes are routinely used in optometry practices worldwide and are safe to use.

- **Confocal microscopy**

A confocal microscope will be used to visualise the corneal sub-basal corneal nerves and dendritic cell in vivo. A probe that emits harmless laser light will come in contact with the transparent front part of the eye for approximately 5 minutes, and microscopic images of the cornea will be captured. Images will be captured from the right eye only. To avoid any discomfort to the patient or causing abrasions on the transparent surface of the eye a topical anaesthetic will be installed in the tested eye and a soft lubricating gel will be applied over the microscope probe.

All the above-mentioned clinical procedures (except the Skin Prick Test) will be repeated for the eligible participants at the follow-up visits.

Reference list

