- Formulation: Prednisolone sodium phosphate 0.5% w/v as well as disodium edetate, monobasic sodium phosphate, sodium chloride, sodium hydroxide and purified water.
- Packaging /units per package: Each unit contains approximately 0.5mL solution in a container that has a twist and pull cap. Each unit should be discarded after a single use. The solution has a neutral pH.
- Storage (incl. specific storage guidance): prednisolone phosphate is stored between 2 - 8°C.
- Market authorisation in Australia: Yes.

The control intervention is an unpreserved lubricant eyedrop (Systane Hydration Unit Dose 0.7 ml).

Systane Hydration Unit Dose 0.7 ml (ARTG ID 308516)

- Active substance: Polyethylene Glycol 400 0.4%, Propylene Glycol 0.3%.
- Manufactured by: Alcon Laboratories Australia Pty Ltd.
- Application form: Topical eyedrop.
- Formulation: Sodium hyaluronate, polyethylene glycol 400, propylene glycol, hydroxypropyl guar, sorbitol, aminomethyl propanol, boric acid, sodium borate, potassium chloride and sodium chloride.
- Packaging /units per package: Each unit contains 0.7 ml.
- Storage (incl. specific storage guidance): Systane Hydration is stored 5 - 25°C.
- Market authorisation in Australia: Yes.

The washout eyedrops is an unpreserved lubricant eyedrops (Blink Intensive Tears Protective Eye Drops - Unit Dose - Lubricant, eye)

Blink Intensive Tears Protective Eye Drops - Unit Dose - Lubricant, eye (ARTG ID 158805)

- Active substance: Polyethylene Glycol 400 0.25%
- Manufactured by: Johnson & Johnson Surgical Vision Inc.
- Application form: Topical eyedrop.

- Formulation: 0.25% polyethylene glycol 400 (PEG 400), purified water, boric acid, sodium hyaluronate, potassium chloride, sodium chloride, sodium borate, calcium chloride, magnesium chloride.
- Packaging /units per package: Each unit contains 0.4 ml.
- Storage (incl. specific storage guidance): Systane Hydration is stored less than 25°C.
- Market authorisation in Australia: Yes.

Ocular lubricant eyedrops (Blink Intensive Tears eyedrops) will be provided to all participants during the washout period and will be asked to install two drops daily in both eyes for 1 week. All medications used in this trial are unpreserved to minimise the possibility of these preservatives impacting the trial results. Only trained optometrists are to be delegated these responsibilities. All medications given in this trial will be prescribed by registered optometrists.

12. Storage, dispensing and product accountability.

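### One participant in three gets prednisolone 0.5% in both eyes, yet no eligibility criterion names glaucoma, ocular hypertension or a past steroid pressure response, and no rule uses the pre-dose pressure reading

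*Protocol*

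**What the plan says.** Sections 8 and 13 of the Protocol allocate 90 participants 1:1:1, so 30 receive the corticosteroid. Section 11 identifies it as prednisolone sodium phosphate 0.5%. Section 14 has participants put one drop in each eye twice a day for two weeks, starting after the baseline visit.

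The eye conditions excluded in 9.2 include "All other ocular surface diseases except allergic conjunctivitis", "Ocular diseases that involve the cornea" and "Active intraocular inflammation". Corneal refractive surgery and regular contact lens wear are also excluded. The only exclusion that concerns a past reaction to the study drops is "Previous allergic reaction to any component of topical eyedrops used in this study including benzalkonium chloride preservative".

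Other provisions bear on who gets in:
- Section 9.4, on screening: "They will take part in a preliminary examination which includes visual acuity assessment and ocular health check in order to exclude undiagnosed eye diseases".
- Section 10, on history taking: "A review of demographics, ocular and medical history will be conducted verbally".
- Section 11: "All medications given in this trial will be prescribed by registered optometrists".
- Section 14 excludes people who use eye or general medication known to affect the health or comfort of the eye.

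Table 1 in section 14 marks Perkins tonometry at Visits 2 to 7.

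**The concern.** Topical corticosteroids can raise intraocular pressure. The Protocol does not say so, and I take it from general clinical knowledge. On that assumption, the people one would want to keep off the steroid arm are those with glaucoma, those with ocular hypertension, and those whose pressure has risen on steroids before. The eligibility list is silent on all three. The trial measures pressure before the first dose but attaches no rule to the result.

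What is at stake is participant safety at entry. Without a stated rule, whether such a person is stopped depends on the clinician who sees them. Investigators and staff are blinded, so no one can take extra care with the steroid arm alone. A rule applied to everyone before dispensing is the natural protection.

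**Working it through.** **1. Share exposed.** 1:1:1 allocation of 90 gives 90/3 = 30 on the corticosteroid, which matches the Protocol's own figure of 30 per arm. The chance of the steroid for any randomised person is 30/90 = 1/3.

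**2. Exposure.** Under the section 14 instruction: 2 drops a day × 14 days = 28 drops per eye, and 28 × 2 eyes = 56 in total. Section 7 calls the dosing biweekly. If that meant twice a week, it would be 2 × 2 weeks = 4 drops per eye. Section 14 is the explicit instruction, so I use it. The omission is the same under either reading.

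**3. Criteria.** 4 inclusion (9.1) + 13 exclusion (9.2) = 17. The number naming glaucoma, ocular hypertension, intraocular pressure or a steroid pressure response is 0. The nearest candidates do not reach these conditions:

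| Criterion in 9.2 | Does it cover raised pressure or a steroid response? |
|---|---|
| No. 6, reaction to the drops | No; allergic reactions only |
| No. 9, other ocular surface disease | No; surface only |
| No. 10, corneal disease | No; cornea only |
| No. 11, intraocular inflammation | No; inflammation, not pressure |
| No. 12, corneal refractive surgery | No |

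**4. Timing of the pressure reading.** Section 7 gives 7 visits including eligibility. Section 14 gives 5 follow-up visits (24 hours and days 7, 14, 21 and 28). 7 − 1 − 5 = 1 baseline visit, which is Visit 2. Drops are given after it, so of the 6 scheduled readings (Visits 2 to 7), 1 is pre-dose and 5 come after dosing starts.

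A reading at Visit 1 cannot be ruled out. Section 10 states "All the above-mentioned clinical procedures (except the Skin Prick Test) will be repeated for the eligible participants at the follow-up visits", which implies an earlier measurement. Table 1 also leaves blank the Visit 1 acuity test that 9.4 requires, so its blanks prove nothing.

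**5. Use of the reading.** No inclusion or exclusion criterion refers to it. Section 9.6 defines worsening by the symptoms and signs score, not by pressure. The list of medication harms in 15.1 includes cataract but not raised pressure.

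**6. Who remains eligible.**

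| Provision | Whom it could stop | Whom it leaves |
|---|---|---|
| Eye check (9.4) | Undiagnosed eye disease, if the check finds it; its content is not stated | A past steroid response; diagnosed but untreated disease |
| Medication rule (14) | Probably drug-treated glaucoma | Untreated raised pressure; a past response in someone now off steroids |
| History (10) and optometrist prescribing (11) | May bring the fact to light | No text says that the fact makes the person ineligible |

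**The case against.** The strongest reply is that the Protocol screens more than the count of 17 suggests. The eye check in 9.4 is meant to exclude people and is not confined to the surface or the cornea. Undiagnosed glaucoma is an eye disease on any plain reading, and glaucoma treated with drops is probably caught by the medication rule. Both rules sit outside the two lists that were counted.

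There are also safeguards after entry. The investigator may withdraw anyone in that person's interest (9.6), a qualified physician assesses non-serious events (15.2), and emergency unblinding is available (section 13). Pressure is read five times after dosing starts, and treatment lasts only two weeks. Finally, the documents do not mention a pressure effect of steroids, and no harm has been quantified.

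Much of this stands. It would be wrong to say that glaucoma goes unscreened. What remains is narrower: untreated ocular hypertension, diagnosed but unmedicated disease, and a past steroid response. The safeguards after entry limit the consequences, but they act only once the person has been exposed and rest on individual judgement. None of them is an entry rule. Eligibility is fixed in the protocol, so this is not a detail left to the SAP.

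**Conclusion.** The point holds as a cheap improvement. None of the 17 listed criteria addresses intraocular pressure, glaucoma or a past steroid pressure response, and no entry or withdrawal rule uses the pressure reading taken before dosing. A person with untreated raised pressure or a past steroid response can be randomised under the criteria as written, with a 1 in 3 chance of 28 steroid drops in each eye.

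This rests on one assumption from outside the documents, that topical corticosteroids can raise intraocular pressure. I make no claim about how many such people would enrol or how often harm would follow. The endpoint, type I error and power are not affected.

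**What to change.** In 9.2, add glaucoma, ocular hypertension and a previous intraocular pressure response to steroids as exclusions. Require the Visit 2 tonometry reading to lie within a limit set by the qualified physician before any drops are dispensed.

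Two small additions belong with this. List raised intraocular pressure among the medication harms in 15.1. Refer any on-treatment reading above the limit to the qualified physician, in all three arms and without unblinding.

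No new visit, device or test is needed, since the pre-dose reading and the ocular history are already planned. The cost is a protocol amendment with ethics approval, matching changes to the emailed screening questions, and a modest referral duty for the physician. A few volunteers become ineligible, some only after completing the one-week washout. Asking about these conditions in the screening questions would bring the known cases to light before the washout.
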